## 6.9 Efficacy Analysis

### 6.9.1 Primary Efficacy Endpoint

The change from baseline at Week 24 of the percentage fat content of the liver measured by MRI will be analyzed by analysis of covariance (ANCOVA) in the Full Analysis Set Population with treatment group and diabetes stratum as factors and baseline MRI value as a covariate. The comparisons will be (1) between the response of the JKB-121 5 mg group and the response of the Placebo group and (2) between the response of the JKB-121 10 mg group and the response of the Placebo group. The least-squares means, standard errors, and 95% confidence intervals for each treatment group and for each comparison will be provided. The two-sided p-values testing for significance within treatment group change from baseline and comparisons between treatment groups will be presented. No multiple comparisons techniques will be applied. The sample SAS code can be found below:

```
*****
Note:
  TREATMENT = 0, (placebo), 1 (JKB-121 5 mg), 2 (JKB-121 10 mg)
  DIABSTAT = nondiabetic, diabetic
  BASE: baseline percentage fat content of the liver measured by MRI
  CHG: change from baseline to Week 24 in the percentage fat content of
       the liver measured by MRI
*****;
proc glm data=MRI;
  class TREATMENT DIABSTAT;
  model CHG = TREATMENT DIABSTAT BASE / ss1 ss3;
  means TREATMENT;
  lsmeans TREATMENT / cov stderr pdiff cl;
  estimate "JKB-121 5 mg : Placebo" TREATMENT -1 1 0;
  estimate "JKB-121 10 mg : Placebo" TREATMENT -1 0 1;
run;
```

The data and model residuals will be inspected for normality and homogeneity of variance, and a logarithmic transformation will be applied if necessary.

To handle missing results such as due to early termination, multiple imputation will be performed. The detailed steps are specified below.

Step 1: Prepare the data for multiple imputation. Since there is only one intermediate visit (Week 12) for MRI collection, the missing pattern would be monotone if endpoint values are not available.

Step 2: PROC MI would be used to impute the missing MRI values. The treatment, diabetes stratum, and MRI values at baseline and all available post-baseline visits would be included. The SAS code can be found as below:

```
PROC MI data=MRI out=MI_OUT nimpute=1000 seed=12345 minimum=0;  
  var TREATMENT DIABSTAT BASE WEEK12 WEEK24;  
  mcmc initial=em prior=jeffreys nbiter=200 niter=500 chain=single;  
run;
```

Step 3: Endpoint would be calculated by averaging the values of Week 12 and Week 24. For each imputation, the ANCOVA model specified above would be performed to compare the change from baseline to Week 24 endpoint between JKB-121 5 mg group the placebo group, and between JKB-121 10 mg group and the placebo group.

Step 4: The procedure PROC MIANALYZE would be used with estimated statistics (“least-squares means”) and associated standard error from each simulation for overall testing results. The overall least-squares means, standard errors, 95% confidence intervals, and p-values would be reported.

The same analysis will be repeated for the mITT and Per Protocol Populations. Multiple imputation will not be performed for the Per Protocol Population; only subjects with both baseline and endpoint will be included in the analysis.

The percentage of fat content of the liver measured by MRI at Baseline and Week 24 will be summarized descriptively, as well as the change from baseline.

The same descriptive statistics and ANCOVA model as the primary efficacy endpoint will be applied to the percentage of fat content of the liver measured by MRI at Baseline and Week 12.

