6. STUDY DESIGN

This is a randomized, double-blind, placebo controlled, parallel-group, phase II trial of JKB-121 in treating subjects with biopsy-proven NASH.

[figure not shown]
Subjects will be randomized at study entry to placebo twice daily, 5 mg twice daily, or 10 mg twice daily of JKB-121 orally to improve NASH with regard to biochemical and MRI/MRS features of NASH in a 1:1:1 ratio.

- Treatment Group 1: placebo twice a day orally
- Treatment Group 2: 5mg of JKB-121 twice a day orally
- Treatment Group 3: 10 mg of JKB-121 twice a day orally

The maximum time on study drug for each subject is 24 weeks with an additional 4 weeks of follow-up.

This allocation is shown diagrammatically in Figure 1

Figure 1: Study Schema

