13.2.1. Analysis of Continuous Variables

Continuous variables will be summarized with descriptive statistics (i.e., sample size, mean, standard deviation, minimum, maximum, median, and quintiles). The continuous variables will be analyzed using a general linear model to test the treatment effect of the changes from pre- to post-treatment [29].

If the data are not transformable to symmetry, rank methods such as the Friedman rank test will be used. The possible transformation will be applied on the original pre- and post-treatment values only.

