### 6.9.2.2 Liver Function

The same descriptive statistics, ANCOVA model, and multiple imputation as the primary efficacy endpoint will be applied to serum aspartate aminotransferase (AST), ALT, and gamma-glutamyl transpeptidase (GGT) at each scheduled visit for the Full Analysis Set Population and the mITT Population.

As a sensitivity analysis, the change from baseline in AST, ALT, and GGT will be analyzed using a mixed-model repeated-measures (MMRM) ANCOVA model for the Full Analysis Set Population, implemented using SAS® Proc Mixed. The factors in the model will be diabetes stratum, treatment group, baseline value, visit, and the treatment group by visit interactions. An unstructured covariance matrix will be used (TYPE=UN). No imputation will be performed. The sample SAS code can be found below:

```
*****
Note:
  USUBJID = unique subject identifier
  TREATMENT = 0, (placebo), 1 (JKB-121 5 mg), 2 (JKB-121 10 mg)
  DIABSTAT = nondiabetic, diabetic
  VISIT = visit
  BASE = baseline value
  CHG = change from baseline to the specified visit
*****;
proc mixed;
  class USUBJID DIABSTAT TREATMENT BASE VISIT;
  model CHG = DIABSTAT TREATMENT BASE VISIT TREATMENT*VISIT;
  Repeated VISIT / TYPE=UN sub=USUBJID;
  lsmeans VISIT*TREATMENT / cl pdiff slice=VISIT;
run;
```

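### The scale of the primary MRI result can be changed after residuals are inspected, by a log rule that is left undefined, and the protocol's only named rank fallback does not compare parallel arms

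*SAP*

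**What the plan says.** SAP 6.9.1 fits a single model to the primary endpoint, "model CHG = TREATMENT DIABSTAT BASE / ss1 ss3". The note to the code defines the response as "CHG: change from baseline to Week 24 in the percentage fat content of" the liver by MRI, a signed difference. After the code comes the conditional rule: "The data and model residuals will be inspected for normality and homogeneity of variance, and a logarithmic transformation will be applied if necessary". The section says nothing more about transformation.

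Protocol 13.2.1, a general section on continuous variables, does name the target: "The possible transformation will be applied on the original pre- and post-treatment values only". It also gives a further step: "If the data are not transformable to symmetry, rank methods such as the Friedman rank test will be used". The SAP repeats neither sentence and has no rank method for the primary endpoint.

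On design, Protocol 6 states: "This is a randomized, double-blind, placebo controlled, parallel-group, phase II trial of JKB-121 in treating subjects with biopsy-proven NASH". Each subject is randomized to one of three arms.

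For the liver enzymes, SAP 6.9.2.2 says: "The same descriptive statistics, ANCOVA model, and multiple imputation as the primary efficacy endpoint will be applied to" AST, ALT and GGT. It does not say whether the conditional log goes with the model.

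**The concern.** There are two separate weaknesses.

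The first is that the scale of the primary result is not fixed. The SAP makes it depend on a residual check with no stated criterion, and the residuals come from a model that includes treatment. The analyst would know the arms, and could know both sets of results, before settling on a scale. A difference in percentage points of liver fat and a ratio of liver fat answer different questions and can give different p-values.

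The second is that the last-resort method named in the protocol does not fit the design. The Friedman test ranks treatments within blocks that contain every treatment, or repeated measurements within a subject. In this trial each subject supplies data for one arm only.

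At stake is whether the primary p-values can be read as those of an analysis fixed in advance, and whether a usable rank analysis exists if one is wanted.

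**Working it through.** The plan states no figure that depends on this rule, so there is nothing to reproduce. The check sets the sections side by side and adds small illustrations.

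**1. What would be logged.** SAP 6.9.1 names no variable. Protocol 13.2.1 restricts transformation to the pre- and post-treatment values. Inclusion requires liver fat above 6% on MRI, so the log of baseline exists, and the log of any positive Week 24 value exists too. Read together, the documents point to log Week 24 against log baseline.

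**2. What that does to the estimate.** SAP 5.1 frames the primary endpoint as change in percentage fat content, and SAP 6.1 powers the trial for a difference of about 5%. Read as 5 percentage points, that effect has no single equivalent on the ratio scale:
- from a baseline of 40% (the top of the range for which Protocol 11.5 cites linearity): 35/40 = 0.875
- from 18% (an assumed mid-range value): 13/18 = 0.72
- from 6% (the entry threshold): 1/6 = 0.17

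A switch of scale is therefore a change of estimand, not just a different display of the same result.

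**3. What is left open on the log scale.**
- No test, threshold or plot criterion defines when a log is necessary.
- No model is written with a log response and a log baseline covariate.
- No back-transformed estimate is named.
- Step 3 of the imputation averages the Week 12 and Week 24 values. The log of an average exceeds the average of the logs whenever the two values differ, and the SAP does not choose between them.
- The SAP does not say whether the check is made once or in each of the 1,000 imputed data sets.

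**4. When the choice is made.** Residuals from the stated model cannot be computed without treatment codes. The SAP does not provide for a blinded check on pooled data. With 2 dose-versus-placebo comparisons and 2 scales there are 2 × 2 = 4 candidate p-values in the primary population, and no rule decides in advance which 2 count.

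**5. Friedman in this design.** There are three ways to try to apply it.
- *Arms as treatments, subjects as blocks.* Not possible, because each subject has one arm. Blocks would have to be invented by grouping unrelated subjects. A simulation of 2,000 trials used 3 arms of 20, log-normal liver fat with median 18% and log SD 0.4, log-scale arm effects of 0, -0.15 and -0.35, and within-subject log SD 0.3, all assumed. Friedman on arbitrary triplets rejected in 72% of trials, and re-pairing the same subjects at random changed the verdict at 0.05 in 22%. The Kruskal-Wallis test, which needs no pairing, rejected in 84%.
- *Visits as treatments, subjects as blocks.* This tests change over time. With 60 subjects, assumed common log falls of 0.15 at Week 12 and 0.20 at Week 24, and no difference between arms, it rejected in 100% of 2,000 trials.
- *Diabetes strata as blocks, one summary per arm.* With b = 2 blocks and k = 3 arms, the largest possible statistic has rank sums 2, 4 and 6: 12/(2×3×4) × (4+16+36) − 3×2×4 = 28 − 24 = 4. The chi-square p-value on 2 df is exp(−2) = 0.135, and the exact p-value is 1/6. It could never reach 0.05.

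None of the three gives the required comparison of each dose with placebo.

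**The case against.** The strongest reply is that the documents, read together, describe a workable analysis. Protocol 13.2.1 says what is transformed, those values can be logged, and ANCOVA of logged values is a valid between-arm comparison. That stands. A reader might infer from the code that the SAP logs the change score itself, which would be undefined for anyone whose liver fat falls or stays the same. The documents do not support this: the SAP names no variable, and the protocol sentence rules the change score out. Nor can it be said that the plan's remedies as a whole give no valid result.

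On Friedman, the protocol offers it only as an example, in a general section, as a last resort. Protocol 13.2 also leaves the detail to the SAP, and the SAP does not use it. All true, and it limits the practical harm. But Friedman is the only rank method named for continuous data, and the SAP puts nothing in its place for the primary endpoint.

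A reader might also infer that ALT, AST and GGT lose power by staying on the raw scale. The documents do not establish this. They give an SD and an entry floor for ALT only, give no mean ALT, and plan for an additive 30 U/L effect. Any gain from logging depends on assumed skewness and a multiplicative effect, so a log analysis as the default is a preference.

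Finally, the trial is declared exploratory. That excuses the lack of multiplicity adjustment, but it does not make a result-dependent choice of scale interpretable.

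**Conclusion.** The point holds in two parts. First, SAP 6.9.1 lets the primary estimate move from percentage points to a ratio on the strength of residuals that need treatment codes, with no trigger, log-scale model or reported quantity specified. Second, Protocol 13.2.1 names a rank test that does not compare independent arms, and the SAP supplies no alternative for the primary endpoint.

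The size is best described as four candidate primary p-values in place of two. The resulting error inflation was not calculated: it depends on how the choice would be made, and the documents give no SD for liver fat. The Friedman results rest partly on assumed distributions and effects, but the conclusion about Friedman follows from the design alone. Neither part invalidates the planned ANCOVA on untransformed change. Both should be settled before unblinding.

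**What to change.** - **SAP 6.9.1:** fix the primary MRI analysis on untransformed change, whatever the residuals show. Delete the conditional log. Add one pre-specified sensitivity analysis of each dose against placebo, either rank ANCOVA or the van Elteren test stratified by diabetes status, and name which.
- **Protocol 13.2.1:** replace the Friedman test with the same method.
- **SAP 6.9.2.2:** state before unblinding which scale is used for ALT, AST and GGT. If it is the log scale, specify log visit value on log baseline, treatment and diabetes stratum, reported as a geometric mean ratio beside the arithmetic means.

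The cost is a wording change in each document, a few lines of code and one extra table. No data collection changes. If the residuals do turn out badly skewed, the primary analysis stays on a scale that fits less well, and the rank analysis is there to show whether that matters.

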13. STATISTICAL CONSIDERATIONS

13.1 Sample Size Calculation

The study will need to screen approximately 100 subjects to enroll 60 patients with biopsy-proven NAFLD who meet the study inclusion / exclusion criteria. With 20 subjects per treatment group, the study will not be powered for efficacy assessment between the two doses. Based on precision analysis, the proposed sample size will provide the maximum error (defined as the half-way of the width of the 95% confidence interval for the difference (change in liver-biochemistry) between two doses (5 mg twice daily vs 10 mg twice daily dose) allowed.

Presuming the observed difference between two treatment groups is 20%, then the 95% confidence interval for the true mean is given by (2.5%, 37.5%) with 20 subjects in each group.

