### 3.2 Secondary Objectives

The secondary objectives are:

- Determine the pharmacokinetic profile of JKB-121 in nonalcoholic steatohepatitis (NASH)
- Assess the impact of treatment with JKB-121 on metabolic markers
- Assess the impact of treatment on liver enzymes (serum alanine aminotransferase [ALT]) over 24 weeks.
- Establish the recommended dose for future NASH treatment studies.
- To evaluate changes of NASH related biomarkers such as adiponectin, leptin, ghrelin, tumor necrosis factor alpha (TNF-alpha), TGF-beta, hyaluronic acid and matrix metalloproteinase 2 (MMP-2).

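### The imputation code enters treatment as a single 0/1/2 column, so with missing scans and a non-linear dose response the 5 mg effect is pulled towards half the 10 mg effect

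*SAP*

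**What the plan says.** SAP 6.9.1 defines the coding as "TREATMENT = 0, (placebo), 1 (JKB-121 5 mg), 2 (JKB-121 10 mg"). The ANCOVA code declares "class TREATMENT DIABSTAT", which gives each arm its own mean, and it tests each dose against placebo separately.

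Step 2 of the imputation uses the list "var TREATMENT DIABSTAT BASE WEEK12 WEEK24" with "mcmc initial=em prior=jeffreys nbiter=200 niter=500 chain=single". There is no CLASS or BY statement. The text says only that treatment, stratum and the MRI values are included; it gives no indicator coding and no imputation by arm. Step 3 then states: "Endpoint would be calculated by averaging the values of Week 12 and Week 24".

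The imputed data feed the primary Full Analysis Set analysis and its mITT repeat. SAP 6.9.2.2 extends the method: "ANCOVA model, and multiple imputation as the primary efficacy endpoint will be applied to serum aspartate aminotransferase (AST), ALT" and GGT. The Per Protocol analysis uses no imputation.

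**The concern.** MCMC imputation here works from a joint normal model, in which a 0/1/2 column contributes one slope. The imputation model therefore assumes a linear dose trend that the analysis model does not, and the assumption enters the results through every imputed value.

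The 5 mg arm bears the consequence. If both doses work equally, its effect is shrunk and power is lost. If only 10 mg works, 5 mg gains an apparent benefit. Each dose against placebo is a prespecified primary comparison, and a secondary objective is to "Establish the recommended dose for future NASH treatment studies". The protocol concedes that "the study will not be powered for efficacy assessment between the two doses", but the shape of the dose response is still something the trial hopes to learn, and the imputation should not fix it in advance.

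**Working it through.** **Inputs from the documents.** 20 per arm; an effect of about 5 points with about 85% power (SAP 6.1); two-sided 0.05 t-test (stated there for ALT). No liver-fat SD and no dropout rate is given.

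**SD.** Without a stated SD the 85% cannot be reproduced, only inverted. Normal approximation: 5 / [(1.960 + 1.036) × √(2/20)] = 5.28. With the t-test: 5.14. The complete-data standard error of a difference is then 5.14 × √(2/20) = 1.63.

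**Assumptions.** Week 12 effect half the Week 24 effect; Week 12 to Week 24 correlation 0.7; equal missingness per arm unless stated. The lower bound of zero on imputed values was not modelled in the independent re-run in step 5.

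**1. Where the line falls.** With equal observed numbers and arm effects (0, m₁, m₂), the least-squares slope on 0/1/2 is m₂/2. Imputed 5 mg minus placebo is m₂/2 whatever m₁ is. For (0, -5, -5) the fitted values are -0.83, -3.33, -5.83, a step of -2.5.

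**2. Both post-baseline scans missing in a share f.** Estimate = (1 - f)·m₁ + f·m₂/2. At f = 20%: 0.8(-5) + 0.2(-2.5) = -4.5. On the Step 3 average the true effect is (-2.5 - 5)/2 = -3.75, and 0.8(-3.75) + 0.2(-1.875) = -3.375.

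| Missing both | 5 mg, both doses at -5 | 5 mg, only 10 mg works | Bias on Step 3 average |
|---|---|---|---|
| 10% | -4.75 | -0.25 | 0.19 |
| 20% | -4.50 | -0.50 | 0.37 |
| 30% | -4.25 | -0.75 | 0.56 |

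**3. Only Week 24 missing.** Given Week 12, the part of the Week 24 effect left to the treatment term is -5 - 0.7(-2.5) = -3.25. Half of it is misplaced, so the bias is about 0.1 × 1.625 = 0.16 at 10% and 0.32 at 20%. On the average it is half that: 0.08 and 0.16.

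**4. Unequal missingness (10/20/30% in placebo/5 mg/10 mg, both scans).** With both doses at -5, the weighted line is -0.74, -3.34, -5.95. The 10 mg contrast is 0.7(-5) + 0.3(-5.95) - 0.1(-0.74) = -5.21, overstated by about 0.2. If only 10 mg works, the line is 0.74, -1.66, -4.05 and the contrast is 0.7(-5) + 0.3(-4.05) - 0.1(0.74) = -4.79, understated by about 0.2.

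**5. Simulation check of the bias.** With 200,000 per arm, SD 5.2 and correlation 0.6, the numeric column gave -4.76, -4.51, -4.26 at 10, 20, 30% missing both scans (both doses at -5), and -0.23, -0.48, -0.74 (only 10 mg works). With only Week 24 missing at 20% it gave -4.68. Dose indicators at 20% missing both gave -5.02 and 0.02. Under a linear response there was no bias (-2.49 against -2.5).

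**6. Power for 5 mg, both doses at -5** (20 per arm, SD 5.14, correlation 0.7, 3,000 trials, 25 imputations, Rubin's rules, both scans missing):

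| Missing both | Week 24: numeric / indicators | Step 3 average: numeric / indicators |
|---|---|---|
| 10% | 78% / 80% | 58% / 63% |
| 20% | 66% / 73% | 47% / 55% |

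At 20% on Week 24, the numeric column gave mean -4.47, sampling SD 1.55 and reported standard error 1.88. Indicators gave -5.00, 1.82 and 1.90. When only 10 mg works, rejection for 5 mg was 2.6% (numeric) and 3.8% (indicators).

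**The case against.** The strongest reply is that a linear term is a reasonable bias-variance trade with 20 per arm. At 20% missing both scans its root-mean-square error is √(0.53² + 1.55²) = 1.64, against 1.82 with indicators. That is true. But the reported standard error stays at 1.88 against 1.90, so the confidence interval does not narrow and power falls. The sponsor takes the bias with almost no visible gain in precision.

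Other points stand and limit the size:

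- **False positives.** The rate is not raised, and bias is zero under the null or a linear response.
- **Missing pattern.** Losing both scans is the unfavourable case. Protocol 6.3.1, 10.4.4 and 10.4.6 try to bring early leavers back for end-of-treatment procedures, which include MRI. With only Week 24 missing, power for 5 mg is about 79% against 80% at 10% missing and 74% against 79% at 20%, with simulation error of about 1.3 points.
- **Other analyses.** The Per Protocol ANCOVA and the MMRM for liver enzymes use no imputation and treat arms as a factor. They help show whether imputation drives a result, but neither replaces the primary analysis.
- **Unstated recoding.** Diabetes status is described in words and must be made numeric for MCMC, so some data preparation is implied. Nothing says it extends to treatment.
- **Exploratory aim.** A shift of 0.15 to 0.3 standard errors in one contrast is unlikely by itself to decide a dose.

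Protocol 13.2 says that values missing through early termination are not imputed. The SAP nevertheless specifies imputation for the primary analysis, so this does not remove the problem.

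**Conclusion.** The concern holds. As printed, the imputation model is more restrictive than the ANCOVA it feeds, and no other section corrects it. With both scans missing in 10 to 20% of each arm, the 5 mg estimate moves by 0.25 to 0.50 points on a 5-point effect, or 0.15 to 0.3 standard errors. With Week 12 observed the shift is 0.16 to 0.32. The bias needs both missing scans and a non-linear dose response. The 10 mg contrast moves only if, in addition, missingness differs by arm, and the direction then depends on the dose-response shape.

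The mechanism follows from the code. The sizes depend on the assumed missingness, SD, correlation and Week 12 effect. This is a modest defect that should be corrected; it does not invalidate the trial.

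**What to change.** In Step 2, replace the treatment column with two 0/1 indicators (5 mg, 10 mg) and code diabetes status 0/1, keeping MCMC: `var D5 D10 DIAB BASE WEEK12 WEEK24;`. Say so in the Step 2 text. Use the same indicators for AST, ALT and GGT, where gaps may be intermittent and MCMC should stay. For MRI, monotone regression with treatment and stratum as class variables is an alternative where the pattern is monotone.

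The cost is one line of code, three derived variables and one extra imputation parameter. At 20% missing both scans the reported standard error of the 5 mg contrast rises only from 1.88 to 1.90. The actual sampling SD rises from about 1.55 to 1.82, because 5 mg imputations no longer borrow from the 10 mg arm; reported and actual error then roughly agree.

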1. PROTOCOL SYNOPSIS

NAME OF PRINCIPAL INVESTIGATOR: [name], MPH	PROTOCOL NUMBER: JKB121-001 (Version 4.0)
NAME OF SPONSOR TaiwanJ Pharmaceuticals Co., Ltd	
NAME OF FINISHED PRODUCT: JKB-121	IND 124,082
NAME OF ACTIVE INGREDIENT: Nalmefene hydrochloride	
Study Title	A Randomized, Double-Blind, Placebo Controlled, Parallel-Group, Phase II Trial of JKB-121 for the Treatment of Nonalcoholic Steatohepatitis (NASH).
Lead Investigator:	[name], MPH Duke University
Number of Centers:	Approximately 12 sites—United States only
Study Phase	II
Study Objectives:	
Primary Objectives:	To evaluate the safety and potential efficacy of two dose levels of JKB-121 (5 mg twice daily and 10 mg twice daily) in reducing liver fat compared to placebo.
Secondary Objective:	The secondary objectives are 
Determine the pharmacokinetic profile of JKB-121 in NASHAssess the impact of treatment with JKB-121 on metabolic markersAssess the impact of treatment on liver enzymes (serum ALT) over 24 weeks.Establish the recommended dose for future NASH treatment studies.To evaluate changes of NASH related biomarkers such as adiponectin, leptin, ghrelin, TNF-alpha, TGF-beta, hyaluronic acid and MMP-2.
Exploratory Objective	Investigate the impact of treatment of potentially relevant inflammatory and metabolic biomarkers associated with NASH
Study Endpoints:	
Primary Endpoints:	Safety: Incidence and severity of adverse events and changes in vital signs and clinical laboratory tests Efficacy: Comparative changes in 
Mean changes from baseline in the percentage fat content of the liver measured by magnetic resonance imaging (MRI) at week 24.
Secondary Endpoints:	Pharmacokinetics: 
Serum concentration of JKB-121 over time including but not limited to maximum observed concentrations (Cmax), minimum observed concentration (Cmin) and area under the concentration time curve (AUC) and if feasible half-life (t½) Metabolic markers: 
Body mass index (BMI)

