## 5 EFFICACY ENDPOINTS

### 5.1 Primary Efficacy Endpoint

Mean and absolute changes from baseline in the percentage fat content of the liver measured by magnetic resonance imaging (MRI) at week 24.

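### Step 3 of the imputation procedure averages Week 12 and Week 24 liver fat, so the primary analysis as written does not estimate the declared Week 24 endpoint

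*SAP*

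**What the plan says.** The protocol synopsis gives the efficacy endpoint as "Mean changes from baseline in the percentage fat content of the liver measured by magnetic resonance imaging (MRI) at week 24". SAP 5.1 has the same time point: "Mean and absolute changes from baseline in the percentage fat content of the liver measured by magnetic resonance imaging (MRI) at week 24". SAP 6.9.1 opens in agreement ("The change from baseline at Week 24 of the percentage fat content of the liver measured by MRI will be analyzed"), and the note above its ANCOVA code defines the response variable as "CHG: change from baseline to Week 24 in the percentage fat content of" the liver.

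The same section then adds the missing-data method: "To handle missing results such as due to early termination, multiple imputation will be performed". Steps 1 and 2 impute missing MRI values from treatment, diabetes stratum, baseline, Week 12 and Week 24. Step 3 begins: "Endpoint would be calculated by averaging the values of Week 12 and Week 24". Its next sentence runs the ANCOVA in each imputed data set to "compare the change from baseline to Week 24 endpoint between JKB-121 5 mg group the placebo group", and likewise for the 10 mg dose.

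The Full Analysis Set is the primary efficacy population (SAP 6.3.1). The analysis is repeated in the mITT and Per Protocol populations, but for the latter: "Multiple imputation will not be performed for the Per Protocol Population; only subjects with both baseline and endpoint will be included in the analysis". Week 12 liver fat is a secondary endpoint in its own right (SAP 5.2).

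**The concern.** Four places fix the primary variable at Week 24, and one sentence builds it from two visits. That sentence is the only explicit rule for constructing the endpoint once the data have been imputed. It is not restricted to subjects with an imputed value, so read literally it also replaces a completer's observed Week 24 scan with an average.

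The primary estimate would then blend in a time point that the SAP treats as a separate secondary endpoint, while still carrying a Week 24 label. A late-onset effect would be diluted and a fading effect inflated. The result also feeds a stated objective, the choice of a dose for future NASH studies.

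Two further effects follow:

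- **Per Protocol.** This analysis skips imputation and its members must have a Week 24 MRI, so the natural reading is that it uses Week 24 alone. A difference between the Full Analysis Set and Per Protocol results could then reflect either the population or the endpoint.
- **Liver enzymes.** SAP 6.9.2.2 carries the same imputation to ALT, AST and GGT at each scheduled visit, where a Week 12/Week 24 average has no clear meaning.

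**Working it through.** **Inputs from the documents.** There are 20 subjects per arm, with about 85% power for a difference of about 5% in mean liver-fat change (SAP 6.1). Tests are two-sided at 0.05 (Protocol 13.2). No SD, Week 12 effect or correlation between visits is given for liver fat.

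**The plan's 85%.** It cannot be checked without an SD, so the SD is back-solved. For a two-sample t-test (noncentral t, 38 degrees of freedom), 85% power needs a standardised difference of 0.972, so SD = 5 / 0.972 = 5.14. The normal approximation gives 5.28. The SD of 5.14 is used below as an assumption.

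**What is estimated.** Let D12 and D24 be the dose-minus-placebo effects at the two visits. Baseline is common to both, so averaging the values averages the changes:

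- target = (D12 + D24) / 2
- bias for Week 24 = (D12 − D24) / 2

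This needs no assumption about SD or correlation. The bias is zero only if D12 = D24.

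**Power for the average.** Assume the change has the same SD at both visits, with correlation r between them:

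- SD of the average = 5.14 × √((1 + r)/2), which is 4.45, 4.74 and 5.01 for r = 0.5, 0.7 and 0.9.

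With D24 = 5:

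| D12 | Target | Bias | Power, r = 0.5 | r = 0.7 | r = 0.9 |
|---|---|---|---|---|---|
| 0 | 2.50 | −2.50 | 41% | 37% | 34% |
| 1.25 | 3.13 | −1.88 | 58% | 53% | 49% |
| 2.5 | 3.75 | −1.25 | 74% | 68% | 64% |
| 3.75 | 4.38 | −0.63 | 86% | 81% | 77% |
| 5 | 5.00 | 0 | 93% | 90% | 87% |

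Averaging loses power when D12/D24 is below 2√((1 + r)/2) − 1, which is 0.73, 0.84 and 0.95 for the three correlations. Above that it gains power, but for a different quantity.

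**Fading effect.** With D12 = 5 and D24 = 2.5 the target is (5 + 2.5)/2 = 3.75, and 3.75/2.5 = 1.5, an overstatement of 50%. With D12 = 5 and D24 = 0 the target is 2.5. By symmetry with the first row, a significant result labelled Week 24 would appear 34% to 41% of the time although no Week 24 effect exists.

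**Sensitivity to equal SDs.** If the Week 12 SD is k times the Week 24 SD, the SD of the average is 5.14 × √((1 + k² + 2rk)/4). For D12 = 2.5 and r = 0.5, 0.7, 0.9, k = 0.8 gives power of 82%, 77% and 73%, and k = 1.2 gives 65%, 60% and 55%. The targets do not change.

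**The case against.** The strongest reply is that the SAP contradicts itself rather than adopting an average. The sentence after the averaging rule still speaks of Week 24 and calls on the ANCOVA already specified, whose response is baseline to Week 24. Imputation is introduced only to deal with missing results. The averaging sentence may be a drafting slip that a programmer would ignore. This is fair as far as it goes, but nothing in the documents says which rule prevails, and two programmers could build different primary results from the same text.

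Several narrower points stand as qualifications:

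- The SAP does not say outright that the Per Protocol analysis uses Week 24 alone. It asks for a baseline and an endpoint, and the endpoint is what Step 3 has just defined as the average. The comparability problem is therefore a likely consequence, not a certain one.
- For liver enzymes, the procedure could be read as adapted to each visit. An MMRM without imputation is also planned, but only as a sensitivity analysis.
- The power figures are hypothetical, come from an unadjusted t-test where the plan uses ANCOVA, and can move in either direction. With equal effects and equal SDs, averaging raises power to between 87% and 93%.
- Week 24 liver fat and its change are also summarised descriptively, and Week 12 has its own ANCOVA, so a discrepancy might be noticed. The descriptive table gives no adjusted comparison or p-value.
- The trial calls its objectives exploratory. This is nevertheless its primary efficacy estimate.

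None of these removes the conflict over what the primary analysis measures.

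**Conclusion.** The concern holds. As written, the primary analysis in the Full Analysis Set targets the mean of the Week 12 and Week 24 effects, not the declared Week 24 effect. That conclusion rests on the text alone.

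The size depends on the Week 12 effect, which the documents do not give. With a Week 24 effect of 5 points, the target falls to 3.75 if the Week 12 effect is half as large and to 2.5 if there is none at Week 12. The corresponding power is 64% to 74% and 34% to 41%, against the stated 85%. These power figures assume the back-solved SD of 5.14, equal SDs at the two visits and a correlation of 0.5 to 0.9. There is no bias only if the two effects are equal. This must be fixed, because it decides what the primary result measures.

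**What to change.** Delete the averaging sentence from Step 3. In each imputed data set, compute the response as Week 24 minus baseline, using the observed Week 24 value where there is one and the imputed value otherwise. Fit the ANCOVA already specified, and pool the two dose-minus-placebo differences in PROC MIANALYZE. State that the Per Protocol analysis uses the same Week 24 variable. Keep Week 12 as its own secondary analysis. In SAP 6.9.2.2, say that ALT, AST and GGT are imputed and analysed using each visit's own value. If the sponsor wants an average over visits, define it as a separately labelled supportive endpoint before unblinding.

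Before unblinding the core change costs one SAP sentence and one line of code, with no operational effect. If the analysis has already been run, the clinical study report should say which definition was used and document any departure from the SAP, as SAP section 2 requires.
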